3.1.5. Pharmacokinetic (PK) Analysis Sets

The Pharmacokinetic Analysis Sets include all enrolled subjects who took at least 1 dose of study drug and have at least 1 nonmissing postdose concentration value reported by the PK laboratory. This is the primary analysis set for all PK analyses.

This analysis set will be used in the analysis of ENTO plasma pharmacokinetic.

3.2. Subject Grouping

Unless otherwise specified, subjects will be grouped by dose level and overall for all analyses.

3.3. Strata and Covariates

Not applicable.

3.4. Examination of Subject Subsets

Not applicable.

3.5. Multiple Comparisons

Not applicable.

3.6. Missing Data and Outliers

3.6.1. Missing Data

In general, missing data will not be imputed unless methods for handling missing data are specified. Exceptions are presented in this document.

The handling of missing or incomplete date for AE onset is described in Section [7.1.5.2](#), and for prior medication and concomitant medication in Section [7.4](#).

3.6.2. Outliers

Outliers will be identified during the data management and data analysis process, but no sensitivity analyses will be conducted. All data will be included in the data analysis.

3.7. Data Handling Conventions and Transformations

In general, age (in years) on the first dosing date of study drug will be used for analyses and presentation in listings. For enrolled subjects who are not dosed with any study drug, the enrollment date will be used instead of the first dosing date of study drug. For screen failures, the date the informed consent was signed will be used for age calculation. If only the birth year is collected on the CRF, “01 July” will be used for the unknown birth day and month for the purpose of age calculation. If only birth year and month are collected, “01” will be used for the unknown birth day.

Non-PK laboratory data that are continuous in nature but are less than the lower limit of quantitation (LOQ) or above the upper LOQ will be imputed as follows:

- A value that is 1 unit less than the LOQ will be used to calculate descriptive statistics if the datum is reported in the form of “< x” (where x is considered the LOQ). For example, if the values are reported as < 50 and < 5.0, values of 49 and 4.9, respectively, will be used to calculate summary statistics. An exception to this rule is any value reported as < 1 or < 0.1, etc. For values reported as < 1 or < 0.1, a value of 0.9 or 0.09, respectively, will be used to calculate summary statistics.
- A value that is 1 unit above the LOQ will be used to calculate descriptive statistics if the datum is reported in the form of “> x” (where x is considered the LOQ). Values with decimal points will follow the same logic as above.
- The LOQ will be used to calculate descriptive statistics if the datum is reported in the form of “≤ x” or “≥ x” (where x is considered the LOQ).

Plasma concentration values that are below the limit of quantitation (BLQ) will be presented as “BLQ” in the concentration data listing. Values that are BLQ will be treated as 0 at pre-dose time points, and one-half the value of the LOQ at post-baseline time points.

The following conventions will be used for the presentation of summary and order statistics:

- If at least 1 subject has a concentration value of BLQ for the time point, the minimum value will be displayed as “BLQ.”
- If more than 25% of the subjects have a concentration data value of BLQ for a given time point, the minimum and Q1 values will be displayed as “BLQ.”
- If more than 50% of the subjects have a concentration data value of BLQ for a given time point, the minimum, Q1, and median values will be displayed as “BLQ.”
- If more than 75% of the subjects have a concentration data value of BLQ for a given time point, the minimum, Q1, median, and Q3 values will be displayed as “BLQ.”
- If all subjects have concentration data values of BLQ for a given time point, all order statistics (minimum, Q1, median, Q3, and maximum) will be displayed as “BLQ.”

3.8. Analysis Visit Windows

3.8.1. Definition of Study Day

Study day will be calculated from the first dosing date of study drug and derived as follows:

- For post-treatment study days: Assessment Date – First Dosing Date + 1
- For days prior to the first dose: Assessment Date – First Dosing Date

Therefore, Study Day 1 is the day of first dose of study drug administration.

Baseline is defined as the last non-missing record on or prior to the date/time of the first dose of study treatment, unless otherwise specified.

3.8.2. Analysis Windows

The nominal visit as recorded on the CRF will be used when data are summarized by visit and no analysis window will be derived.

4. SUBJECT DISPOSITION

4.1. Subject Enrollment and Disposition

A summary of subject enrollment will be provided by dose level for each country and overall based on all enrolled subjects. The summary will present the number and percentage of subjects enrolled. For each column, the denominator for the percentage calculation will be the total number of subjects analyzed for that column.

A summary of subject disposition will be provided by dose level based on FAS. This summary will present the number and percentage of subjects in the following categories:

- ENTO discontinuation
 - Reasons of ENTO discontinuation
- VCR discontinuation
 - Reasons of VCR discontinuation
- Dexamethasone discontinuation
 - Reasons of dexamethasone discontinuation
- CNS prophylaxis discontinuation
 - Reasons of CNS prophylaxis discontinuation
- Included in the DLT analysis set
- Study discontinuation
 - Reasons of study discontinuation

The denominator for the percentage calculation will be the total number of subjects in FAS corresponding to that column.

A data listing of all enrolled subject enrollment to describe the site, subject number, date of first and last dose and dose level of ENTO, analysis set inclusion (FAS and DLT analysis sets), reasons for all study drugs' discontinuation, and reasons for study discontinuation will be provided.

4.2. Extent of Study Drug Exposure and Adherence

Extent of exposure to study drug will be examined by assessing the total duration of exposure to study drug and the level of adherence to the study drug specified in the protocol. The summaries will be based on Safety Analysis Set.

4.2.1. Duration of Exposure to Study Drugs

Total duration of exposure to study drugs will be defined as last dosing date minus first dosing date plus 1, regardless of any temporary interruptions in study drug administration, and will be expressed in weeks using up to 1 decimal place (eg, 4.5 weeks).

The duration of exposure to ENTO, VCR, dexamethasone, and CNS prophylaxis will be summarized respectively using descriptive statistics. Besides, the number and percentage of subjects exposed to each drug will be presented as follows:

- ENTO: at least 1 day, 14 days, 21 days, 28 days, and 2, 3, 6, 9 months, etc.
- VCR: Cycle 1, Cycle 2, Maintenance Cycle 1, Maintenance Cycle 2, etc.
- Dexamethasone: Cycle 1, Cycle 2, Maintenance Cycle 1, Maintenance Cycle 2, etc.
- CNS prophylaxis: Cycle 1, Cycle 2

The number and percentage of subjects who have dose modification and dose interruption will also be summarized.

4.2.2. Adherence (Compliance) with Study Drugs

By-subject listings of ENTO accountability (dispenses and returns), VCR administration, dexamethasone administration, CNS prophylaxis administration, dose interruption, and dose modification will be provided by subject ID number (in ascending order) and visit (in chronological order).

4.3. Protocol deviations

Subjects who did not meet the eligibility criteria for study entry, but enrolled in the study will be identified regardless of whether they were exempted by the sponsor or not. A by-subject listing will be provided for those subjects who did not meet at least 1 eligibility (inclusion or exclusion) criterion. The listing will present the eligibility criterion (or criteria if more than 1 deviation) that subjects did not meet and related comments, if collected.

Protocol deviations occurring after subjects entered the study are documented during routine monitoring. A by-subject listing will be provided for those subjects with important protocol deviation.

5. BASELINE CHARACTERISTICS

The baseline characteristics will be presented by dose level and overall based on FAS.

5.1. Demographics

Subject demographic variables (ie, age, sex, race, and ethnicity) will be summarized using descriptive statistics for age, and using number and percentage of subjects for sex, race, and ethnicity.

A by-subject demographic listing, including the informed consent date, will be provided by subject ID number in ascending order.

5.2. Other Baseline characteristics

Other baseline characteristics include body weight (in kg), height (in cm), body mass index (BMI; in kg/m^2), ECOG status, and cytogenetics. BMI will be calculated by the formula:

$$\text{BMI (kg/m}^2\text{)} = \text{weight} / (\text{height}^2) \text{ (round to 1 decimal point).}$$

Other baseline characteristics will be summarized using descriptive statistics.

A by-subject listing of other baseline characteristics will be provided by subject ID number in ascending order.

5.3. Medical History

Medical history will be collected at screening for disease-specific and general conditions (ie, conditions not specific to the disease being studied). General medical history data will not be coded.

A by-subject listing of disease-specific (including hematologic malignancy type, date of initial diagnosis, and detailed diagnosis) and general medical history will be provided separately by subject ID number in ascending order.

5.4. Prior Anticancer Therapy

A by-subject listing of prior anticancer therapy and prior radiation therapy will be provided separately by subject ID number in ascending order.

6. EFFICACY ANALYSES

Efficacy will be evaluated per the response criteria in NCCN guidelines on ALL Version 2, 2016. The major criteria for judging response will include physical examination and examination of blood and bone marrow. All laboratory studies that are abnormal prior to study will be repeated to document the degree of maximal response.

For subjects with extramedullary disease (EMD) if these are the only sites of evaluable disease (no BM involvement) to evaluate disease status and response, imaging (computerized tomography (CT) with contrast or positron emission tomography (PET)) should be performed. Imaging will be evaluated using NCCN guideline Version 2, 2016.

Clinical response will be evaluated with investigator assessments. All efficacy endpoints will be analyzed by dose level using FAS.

6.1. Primary Efficacy Endpoints

Not applicable.

6.2. Secondary Efficacy Endpoints

6.2.1. Definition of the Secondary Efficacy Endpoints

- Overall Remission (CR or CRi) rate at end of induction - defined as the proportion of subjects who achieve complete remission (CR) or complete remission with incomplete hematologic recovery (CRi) at the end of induction
- Complete remission (CR) rate at the end of induction - defined as the proportion of subjects who achieve CR at the end of induction
- Partial response (PR) rate at end of induction - defined as the proportion of subjects who achieve a partial response of marrow or by imaging criteria for patients with extramedullary disease (NCCN guidelines version 2.2016) as the best response
- Overall Response (CR, CRi, or PR) rate at end of induction - defined as the proportion of subjects who achieve a complete remission (CR), complete remission with incomplete hematologic recovery (CRi) or partial response (PR) at end of induction

6.2.2. Analysis Methods for Secondary Efficacy Endpoints

Overall Remission (CR/CRi) rate, CR rate, PR rate, and Overall Response rate (CR, CRi, or PR) on or prior to other anticancer therapy and HSCT (if there is) at the end of induction will be summarized by dose level and overall. The number and percentage of subjects will be presented.

A by-subject listing of response assessment and EMD assessment will be provided by subject ID number (in ascending order) and visit (in chronological order).

7. SAFETY ANALYSES

Safety analyses will be conducted using Safety Analysis Set, unless otherwise specified.

7.1. Adverse Events and Deaths

7.1.1. Adverse Event Dictionary

Clinical and laboratory adverse events (AEs) will be coded using the current version (ie, Version 20.1) of Medical Dictionary for Regulatory Activities (MedDRA). System organ class (SOC), high-level group term (HLGT), high-level term (HLT), preferred term (PT), and lower-level term (LLT) will be provided in the AE dataset.

7.1.2. Adverse Event Severity

Adverse events are graded by the investigator as Grade 1, 2, 3, 4, or 5 according to toxicity criteria specified in the Common Toxicity Criteria for Adverse Events (CTCAE) Version 4.03 {[U.S. Department of Health and Human Services 2010](#)}. The severity grade of events for which the investigator did not record severity will be categorized as “missing” for tabular summaries and data listings and the missing category will be listed last in data presentation.

7.1.3. Relationship of Adverse Events to Study Drug

Related AEs are defined as AEs marked by investigators as ‘Related’ on the AE CRF to the questions of ‘Related to Study Treatment GS-9973 SDD’, ‘Related to Study Treatment Dexamethasone’, ‘Related to Study Treatment Vincristine’, ‘Related to Study Treatment Cytarabine Arabinoside’, and ‘Related to Study Treatment CNS Prophylaxis’. Relatedness will always default to the investigator’s choice, not that of the medical monitor. Events for which the investigator did not record relationships to study treatment will be considered related to study treatment for summary purposes. However, by-subject data listings will show the relationship as missing.

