3.5. Dose-Limiting Toxicity

The evaluation period for dose-limiting toxicity (DLT) will occur from the start of treatment through the end of Cycle 1 in the escalation phase. Subjects who fail to complete 21 days of GS-9973 or fail to receive sufficient exposure (> 50% of planned total dose) to VCR and dexamethasone for reasons other than treatment-related toxicity will be considered not evaluable for DLT assessment and additional (replacement) subjects may be enrolled to that dose level in order to provide adequate safety data on which to base dose escalation decisions. All toxicities will be graded using National Cancer Institute (NCI) Common Terminology Criteria for Adverse Events (CTCAE) Version 4.03 (Appendix 3).

The occurrence of any of the following toxicities during Lead-in/Cycle 1 will be considered a DLT if judged by the Investigator to be possibly, probably, or definitely related to the administration of any drug in the treatment regimen (GS-9973, VCR, dexamethasone, institutional standard CNS prophylaxis):

- Grade 4 (or higher) non-hematologic toxicity
- Grade 3 non-hematologic toxicity lasting \geq 7 days despite optimal supportive care
- Any Grade 3 non-hematologic laboratory value if:
 - Medical intervention is required to treat the patient, or
 - The abnormality leads to hospitalization, or
 - The abnormality persists for >1 week

- Grade 4 Neutropenia (ANC < 500 /µl) persistent for greater than 14 days or associated with febrile neutropenia
- Grade 4 thrombocytopenia (platelets < 25,000/µl) persisting for greater than 14 days (or greater than 25,000 /µl, but requiring prophylactic platelet transfusion to maintain this level)

The following will NOT be considered as a DLT for the purposes of this study, regardless of grade:

- Alopecia
- Fatigue
- Nausea or vomiting controllable with anti-emetic therapy
- Catheter-associated venous thrombosis
- Infection (or infection-related toxicities such as fever/sepsis, unless it is felt that the infection resulted from unexpectedly complicated myelosuppression due to study medication)
- Transient electrolyte abnormalities (any grade) that are not clinically significant and are correctable within 24 hours
- Transient liver function test abnormalities (AST, ALT, bilirubin, or alkaline phosphatase) that resolve to \leq Grade 2 within 7 days

Number of subjects with DLT at a given level	Escalation Decision Rule	

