3.5.1. Management of Dose Limiting Toxicities

It is recognized that drug-related toxicity in this population may be difficult to ascertain given the nature of hematologic disease. Investigators will attempt to assign attribution of toxicities to each drug if possible. The Cancer Therapy Evaluation Program (CTEP) Active Version of the NCI Common Terminology Criteria for Adverse Events (CTCAE) version 4.03 will be utilized for AE reporting.

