3.5.2.2. Dose Modifications for Non-Hematologic Toxicity for VCR, and dexamethasone

If the subject experiences any non-hematologic clinically significant Grade 3 or greater toxicity felt to "possibly" be related to any agent, hold the protocol therapy until it resolves to \leq Grade 2. If related to VCR, reduce the dose of VCR to by one dose level (per Table 3-1); if at lowest dose level, resuming treatment with VCR will be at Investigator's discretion after discussion with Sponsor. Refer to product label information for specific toxicity management. If related to dexamethasone, resuming treatment with dexamethasone will be at the discretion of the Investigators. If the toxicity recurs, subject will be removed from study. If protocol therapy is withheld for more than 2 weeks for toxicity possibly, probably, or definitely related to protocol-based therapy or up to 4 weeks for any other reason, subjects will be removed from protocol.

Subjects who have been dose-reduced cannot be returned to a higher dose level.

Toxicities in an individual subject must resolve to Grade 2 or to baseline levels before proceeding with the next cycle of treatment.

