7.2.1. Assessment of Causality for Study Drugs and Procedures

The investigator or qualified subinvestigator is responsible for assessing the relationship to study drug therapy using clinical judgment and the following considerations:

- No: Evidence exists that the adverse event has an etiology other than the study drug. For SAEs, an alternative causality must be provided (eg, preexisting condition, underlying disease, intercurrent illness, or concomitant medication).
- Yes: There is reasonable possibility that the event may have been caused by the investigational medicinal product (study drug GS-9973).

It should be emphasized that ineffective treatment should not be considered as causally related in the context of adverse event reporting.

The relationship to study procedures (eg, invasive procedures such as venipuncture or biopsy) should be assessed using the following considerations:

- No: Evidence exists that the adverse event has an etiology other than the study procedure
- Yes: The adverse event occurred as a result of protocol procedures, (eg., venipuncture)

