7.1.6.1. Summaries of AE Incidence by Severity

The number and percentage of subjects who experienced at least 1 TEAE will be provided and summarized by SOC, HLT, PT, and treatment group. For other AEs described below, summaries will be provided by SOC, PT, and maximum severity:

- TEAEs
- TEAEs of Grade 3 or higher
- Treatment-related TEAEs by study drugs (ie ENTO, VCR, dexamethasone, CNS prophylaxis)
- Treatment-related Grade 3 or higher TEAEs by study drugs

- TE SAEs
- TE treatment-related SAEs by study drugs
- TEAEs leading to treatment discontinuation by study drugs
- TEAEs leading to treatment reductions or interruptions by study drugs
- TEAEs leading to death
- TEAEs leading to study discontinuations

A brief, high-level summary of AEs described above will be provided by the number and percentage of subjects who experienced the above AEs.

Multiple events will be counted only once per subject in each summary. Adverse events will be summarized and listed first in alphabetic order of SOC, and then by PT in descending order of total frequency within each SOC. For summaries by severity, the most severe severity will be used for those AEs that occurred more than once in a given subject during the study.

In addition, data listings will be provided for the following:

- All AEs, indicating whether the event is treatment emergent
- All AEs of Grade 3 or higher
- All SAEs
- Deaths
- All AEs leading to study treatment discontinuation by study drugs

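### SAP 7.1.3 counts a missing causality answer as related without checking exposure, so the by-drug related-AE tables can attribute an event to a drug not yet given

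*SAP*

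**What the plan says.** SAP 7.1.3 builds the related-AE definition from five CRF questions, one each for GS-9973 SDD, dexamethasone, vincristine, cytarabine and CNS prophylaxis. For missing answers it says: "Events for which the investigator did not record relationships to study treatment will be considered related to study treatment for summary purposes". It adds: "However, by-subject data listings will show the relationship as missing". There is no condition on exposure and no statement of how the five answers combine into one overall flag.

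SAP 7.1.6.1 then plans "Treatment-related TEAEs by study drugs (ie ENTO, VCR, dexamethasone, CNS prophylaxis", and repeats the by-drug split for related Grade 3 or higher TEAEs and related SAEs. No cytarabine table is planned.

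The drugs start at different times (SAP 1.2 and Appendix 1; Protocol 3.3.1 and Appendix 2). ENTO is given alone for seven days, then VCR is added, then dexamethasone, and CNS prophylaxis comes at the end of Cycle 1.

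The protocol's instructions on causality are not uniform. Section 7.2.1 defines a Yes answer as: "There is reasonable possibility that the event may have been caused by the investigational medicinal product (study drug GS-9973". Section 3.5 judges DLTs as "related to the administration of any drug in the treatment regimen (GS-9973, VCR, dexamethasone, institutional standard CNS prophylaxis", and section 3.5.1 says: "Investigators will attempt to assign attribution of toxicities to each drug if possible".

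**The concern.** Counting missing causality as related is meant to resolve doubt against the drug. Where the subject had not received the drug when the event began, there is no doubt to resolve. If a Lead-in event has a blank vincristine answer and is tabulated as vincristine-related, the attribution is impossible in time rather than cautious.

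Safety is the primary objective, and these tables are the only planned summaries that separate the contributions of the four components. They are presented by dose level and overall (SAP 3.2), and a dose level holds 3 to 6 subjects. One wrongly flagged subject moves a dose-level rate by 1/6 = 17 to 1/3 = 33 percentage points.

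The wording is also open to two readings. The rule may apply to each blank answer, or only to events with no answer recorded at all. Two programmers could produce different by-drug tables from the same data.

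**Working it through.** The documents give no figure for this point, so there is none to reproduce. The check sets the rule against the dosing schedule.

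**1. First planned dose by study day.** Both schedule appendices place Lead-in Day -7 at study day 1, Cycle 1 Day 1 at day 8, Cycle 1 Day 8 at day 15 and Cycle 1 Day 28 at day 35. CNS prophylaxis has a window of ±3 days, hence days 32 to 38. The Lead-in/Cycle 1 window is study days 1 to 35. Days before first dose = first study day − 1, capped at 35.

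| Drug | First study day | Days before first dose | Share of 35 days |
|---|---|---|---|
| ENTO | 1 | 0 | 0% |
| VCR | 8 | 7 | 7/35 = 20% |
| Dexamethasone | 15 | 14 | 14/35 = 40% |
| CNS prophylaxis | 35 (32 to 38) | 34 (31 to 35) | 34/35 = 97% (89% to 100%) |

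These shares show how long the rule can misattribute. They do not measure how often it does. A subject who stops early may never receive a later drug, so for that drug the exposed period never begins.

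**2. Does the result depend on the reading?**
- If each blank answer triggers the rule, any event in the periods above with a blank for that drug enters that drug's table.
- If only a wholly blank event triggers it, the event is related to study treatment as a whole, and the SAP does not say which of the four tables it enters. If it enters all four, the same misattribution follows. If it enters only an overall flag, the by-drug tables are untouched.

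**3. Illustration of size.** The documents give neither the blank rate nor the number of AEs, so both are assumed. Let a subject have k AEs with onset before the first dose of a drug, and let each answer be blank independently with probability m, with the rule applied per question. Then P(at least one AE wrongly counted as related to that drug) = 1 − (1 − m)^k. Expected numbers are for the 20 subjects planned for escalation.

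| m | k = 1 | k = 5 | k = 10 |
|---|---|---|---|
| 0% | 0 | 0 | 0 |
| 1% | 1.0% (0.2 of 20) | 4.9% (1.0) | 9.6% (1.9) |
| 5% | 5.0% (1.0) | 22.6% (4.5) | 40.1% (8.0) |
| 10% | 10.0% (2.0) | 41.0% (8.2) | 65.1% (13.0) |

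For example, with m = 0.05 and k = 5: 1 − 0.95^5 = 0.226, and 20 × 0.226 = 4.5. A subject who also has a genuinely related AE for the same drug is already in the any-related row, so the net effect on that row would be smaller.

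**The case against.** The default is a familiar, pre-specified and conservative convention. Blanks stay visible in the listings, and with about 20 subjects a reader could trace every imputed case. Protocol 9.1.6 describes monitoring and queries for completeness, so blanks may be rare. All of this stands and limits the size. It does not justify a rule that can assign an event to a drug given only later, and tracing cases through listings does not correct the tables.

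Four stronger conclusions are tempting, and the documents do not support them:
- **That the tables are inflated.** The blank rate is not given, so inflation is possible but not shown. The 20%, 40% and 97% are shares of calendar time, not of AEs or of blank answers.
- **That blanks follow from obeying the protocol, because it asks only about GS-9973.** That describes section 7.2.1 alone. Sections 3.5 and 3.5.1 ask about the other drugs, and section 3.5.2.2 acts on the answer: "If related to VCR, reduce the dose of VCR to by one dose level (per Table 3-1". The CRF also puts a separate question for each drug.
- **That the cytarabine question distorts the by-drug tables.** The CRF has an item "Related to Study Treatment Cytarabine Arabinoside", but no cytarabine table is planned, so it could affect only an overall flag. Nor can cytarabine be called foreign to the regimen, because CNS prophylaxis follows institutional standard with its agents unnamed.
- **That the primary endpoint, or a Lead-in versus combination comparison, is compromised.** DLT relatedness is the investigator's judgement (Protocol 3.5), and SAP 7.1.7 lists the DLT events. This rule does not enter. No Lead-in versus combination comparison is planned (SAP 3.2 and 3.4).

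**Conclusion.** The point holds as a gap in a stated rule. SAP 7.1.3 lets a missing answer count as related to a drug not yet given, or never given, and SAP 7.1.6.1 carries relatedness into separate tables for four drugs with staggered starts. This rests on the rule being applied per question, or on wholly blank events being placed in every by-drug table. The SAP rules out neither.

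The direction is upward for VCR, dexamethasone and CNS prophylaxis. ENTO has no period before exposure among treatment-emergent events during planned dosing. The size is unknown and is zero if all answers are recorded. The point is modest, but worth acting on because the correction costs almost nothing and dose-level denominators are small.

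**What to change.** In SAP 7.1.3:
- Apply the missing-as-related rule separately to each drug, and only when AE onset is on or after that subject's first dose of that drug. Otherwise classify the event as not related (not exposed) for that drug. Where an incomplete onset date leaves the order unknown, keep the conservative default, because the imputation in SAP 7.1.5.2 can place onset at the first ENTO dose.
- Define overall related as related to at least one regimen drug.
- Report the number of imputed answers per drug, for example in a table footnote.
- State how the cytarabine CRF question maps to CNS prophylaxis.
- Note in the SAP or CSR that Protocol 7.2.1 defines causality against GS-9973, while Protocol 3.5 and 3.5.1 and the CRF ask about the other drugs.

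The cost is a few sentences, one date condition in the programming and a footnote. If the SAP is already final, SAP section 1 provides for documenting the change in the CSR. No protocol amendment is needed, since it would require IRB approval and could not alter answers already collected. The downside is that related counts become slightly less conservative, but only for events that began before the drug was given.
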